## 6. STUDY INTERVENTION

A list of the adverse events and potential risks associated with the study intervention administered in this study can be found in Section 10.4, Adverse Events.

### 6.1 ONABOTULINUMTOXINA

#### 6.1.1 STUDY INTERVENTION DESCRIPTION

**Botulinum Toxin (BTX).** BTX is a neurotoxin produced by the bacterium *Clostridium botulinum*, which secretes eight exotoxins, (A, B, C(1), C(2), D, E, F, G), all of which block the release of acetylcholine (the primary neurotransmitter at the neuromuscular junction) by cleaving soluble N-ethylmaleimide sensitive fusion protein (SNAP) Receptors (SNARE), leading to muscle paralysis. BTX (onabotulinumtoxinA; BTX) has been used for decades with great efficacy in multiple conditions, including strabismus, dystonias, spastic movement disorders, headaches, hyperhidrosis, as well as innumerable cosmetic applications such as reducing the prominence of wrinkles. BTX has an excellent safety profile, with one systematic review of 36 randomized controlled trials noting no serious adverse events.

#### 6.1.2 ACQUISITION

OnabotulinumtoxinA (BTX) will be obtained from OHSU research pharmacy services. Where possible, a single manufacturer of generic BTX (Allergan, Dublin, Ireland) will be used throughout the conduct of this trial. However, BTX may be sourced from alternative manufacturers.

#### 6.1.3 FORMULATION, APPEARANCE, PACKAGING AND LABELING

BTX (onabotulinumtoxinA) is an FDA approved drug and available for human use. Each vial of Botox® Cosmetic contains either 100 Units of Clostridium botulinum type A neurotoxin complex, 0.5 mg of Albumin Human, and 0.9 mg of sodium chloride or 50 Units of Clostridium botulinum type A neurotoxin complex, 0.25 mg of Albumin Human, and 0.45 mg of sodium chloride in a sterile, vacuum-dried form without a preservative

#### 6.1.4 PRODUCT STORAGE AND STABILITY

BTX (onabotulinumtoxinA)

#### 6.1.5 COMPATIBILITY

BTX (onabotulinumtoxinA) may only be reconstituted with 0.9% sodium chloride.

#### 6.1.6 PREPARATION

The commercial preparation of BTX (onabotulinumtoxinA) is supplied in vials containing 100 U of the lyophilized powder. The entire required dose of BTX (onabotulinumtoxinA) will be withdrawn from the vial and reconstituted in 1 mL of 0.9% sodium chloride. During this time period, unused reconstituted BTX (onabotulinumtoxinA) should be stored in a refrigerator (2° to 8°C) for up to 24 hours until time of use. BTX (onabotulinumtoxinA) vials are for single-dose only. Used vials of BTX will be discarded. For this trial, the entire required dose of BTX will be withdrawn from each vacuum-dried vial and reconstituted in 1 mL of 0.9% sodium chloride. Endoscopic administration of the drug will be performed by trained endoscopists within 24 hours of reconstitution.

#### 6.1.7 ADMINISTRATION

Endoscopic injection of BTX into the lower esophagus is a well-described treatment for Sphincter of Oddi Dysfunction. Subjects will undergo an outpatient upper endoscopy with injection of BTX into the sphincter of Oddi (Figure 1). The endoscope is introduced through the mouth and advanced to the duodenum. At the level of the ampulla of the Vater, the injection needle will be inserted into the upper margin of the papillary orifice. Then 1 mL of the properly reconstituted BTX (onabotulinumtoxinA) solution will be injected as a single deposit. Then the endoscope will be removed to complete the procedure. Acceptable window of time for administration of agent is the total procedural time during endoscopy. No special IV tubing or filtration is needed.

#### 6.1.8 SPECIAL CONSIDERATIONS FOR ADMINISTRATION

All subjects will have their heart rate, respiratory rate, oxygen saturations, blood pressure and ventilation will be monitored throughout and after the procedure. If subjects develop hypersensitivity symptoms like rash, wheezing, or pruritus, hypersensitivity medications should be administered.

There are no other special considerations, including hydration, steroids, special IV tubing, filtration, or special equipment required.

#### 6.1.9 ACCOUNTABILITY

The Investigator, or a responsible party designated by the Investigator, must maintain a careful record of the inventory and disposition of the study agent. (See the [NCI Investigator's Handbook for Procedures for Drug Accountability and Storage](#)).

Responsibility for drug accountability at the study site rests with the Investigator; however, the Investigator may assign some of the drug accountability duties to an appropriate pharmacist or designee. Inventory and accountability records must be maintained and readily available for inspection by the study monitor and are open to inspection at any time by any applicable regulatory authorities or other oversight bodies.

The Investigator or designee will collect and retain all used, unused, and partially used containers of study medication until full accounting has been completed. The Investigator or designee must maintain records that document:

- Investigational product delivery to the study site.
- The inventory at the site.
- Use by each participant including pill/unit counts from each supply dispensed.
- Return of investigational product to the Investigator or designee.
- Destruction or return of investigational product for final disposal.

These records should include dates, quantities, batch/serial numbers (if available), and the unique code numbers (if available) assigned to the investigational product and study participants.

The investigational product must be used only in accordance with the protocol. The Investigator will also maintain records adequately documenting that the participants were provided the correct study medication specified.

Completed accountability records will be archived by the site. There are no study drugs that require shipment back to the manufacturer at the end of the study.

#### 6.1.10 DESTRUCTION AND RETURN

At the completion of the study, the Investigator or designee will oversee the destruction of study agent per local institutional guidelines.

### 7. TREATMENT PLAN

#### 7.1 DOSAGE AND ADMINISTRATION

Regimen Description					
Agent	Premedication; Precautions	Dose	Route*	Schedule	Cycle Length
onabotulinumtoxinA	none	100 units in 1 mL of 0.9% NaCl solution	Endoscopic injection into intraduodenal sphincter of Oddi segment	Days 7-14 before surgery	Single injection administe red once

*\*Specify route of administration (e.g., IVB, IVP, IVCI, PO, intra-arterial, peritoneal, intrathecal, intracavity, etc.) and duration (e.g., IVP over 10 seconds), including any allowable time windows (+/- minutes).*

Subjects will undergo an outpatient upper endoscopy for administration of a single BTX injection. The endoscope will be introduced through the mouth and advanced to the duodenum. At the level of the Ampulla of the Vater, the injection needle will be inserted into the upper margin of the papillary orifice. Then 1 mL (100 units) of the properly reconstituted BTX solution will be injected as a single deposit. The volume in syringe will be checked to ensure the entire amount is delivered. Then the endoscope will be removed to complete the procedure. Acceptable window of time for administration of agent is the total procedural time during endoscopy. No special IV tubing or filtration is needed. The participant's heart rate, respiratory rate, oxygen saturations, blood pressure and ventilation will be monitored throughout and after the procedure. No additional BTX injection will be administered for each participant. Reported adverse events and potential risks are described in Section 10, SAFETY. No investigational or commercial agents or therapies other than those described below may be administered with the intent to treat

the participant's malignancy.

## 7.2 DISCONTINUATION FROM STUDY INTERVENTION

Study intervention is a one-time dose during endoscopic procedure, thereafter all other procedures and treatment will be in accordance with institutional standard of care.

## 7.3 TREATMENT PERIOD AND MAINTENANCE

Participants will receive BTX (onabotulinumtoxinA) on between 7 to 14 days prior to planned distal pancreas resection. No other study-specific interventions or maintenance dosing will occur.

## 7.4 CONCOMITANT MEDICATION AND SUPPORTIVE CARE GUIDELINES

Supportive measures for optimal medical care are to be given throughout the study as indicated by the treating physician's assessment of the participant's medical need and institutional and general medical guidelines for the care of participants undergoing distal pancreas resections.

Medications required to treat AEs, manage cancer symptoms, concurrent diseases and supportive care agents, such as pain medications, anti-emetics and anti-diarrheals are allowed in general. The participant must be told to notify the investigational site about any new medications begun after the start of the study treatment.

Other medications for the prophylaxis of POPF are disallowed, including hydrocortisone and pasireotide. These medications may be administered at the treating physician's discretion following diagnosis of any POPF.

All medications (other than investigational products) and significant non-drug therapies (including vitamins, herbal medications, physical therapy and blood transfusions) administered during the study must be listed on the case report form (CRF).

Treatment recommendations described in the following sections may be modified according to institutional standards and guidelines as appropriate.

### 7.4.1 NAUSEA / VOMITING

No routine prophylactic anti-emetic treatment is required at the start of treatment, however, participant should receive appropriate anti-emetic treatment at the first onset of nausea or vomiting and as required thereafter per institutional guidelines.

### 7.4.2 HYDRATION

Not applicable to the present study

**7.4.3 OBSERVATION PERIOD** – Patients will be observed and monitored according to the standard of care following upper endoscopy, generally 1-2 hours.

### 7.4.4 MANAGEMENT OF SERIOUS COMPLICATIONS FROM STUDY INTERVENTION

**Pancreatitis:** Any patient with abdominal pain, nausea, and intolerance to oral intake will be evaluated for pancreatitis and managed per the standard of care depending on severity of pancreatitis (see American Gastroenterological Association guidelines).

**Gastrointestinal Bleeding:** Patients reporting hematemesis, hematochezia, or melena following study will be evaluated by phone, in clinic, or the emergency department as their clinical status dictates. Most gastrointestinal bleeding following endoscopy is self-limited and otherwise asymptomatic and not considered a serious complication. If clinically significant bleeding occurs, defined as that accompanied by new anemia, hypotension, or other signs/symptoms of significant blood loss, patients will be further evaluated in the emergency department and treated per the standard of care with serial evaluation of hemoglobin/hematocrit, PT/INR, vitals/physical exam, and receive endoscopic, intra-arterial, or surgical management as indicated.

**Gastrointestinal Perforation:** Patients experiencing new severe abdominal pain following discharge from the endoscopic procedural unit will be evaluated in clinic or in the emergency department as dictated by clinical status. Patients with gastrointestinal perforation will be treated as clinically indicated, typically with surgical intervention.

**BTX-Specific Complications:** Patients experiencing BTX-related complications will be managed according to the clinical scenario. Serious allergy-spectrum reactions (e.g., anaphylaxis) will be noted during the observation period and managed accordingly by the clinical staff. Other reactions such as local weakness are predominantly reported in cases of skeletal muscle-adjacent injections. No specific management is required in most cases, however new-onset symptoms following BTX injections will be evaluated by phone or in clinic as indicated, and managed appropriately.

Patients will be counseled on warning signs for the above serious complications prior to and after BTX injection.

## **7.5 PRECAUTIONARY MEDICATIONS, TREATMENTS, AND PROCEDURES**

Patients will be asked to be *nil per os* starting at midnight prior to planned upper endoscopy.

## **7.6 PROHIBITED MEDICATIONS, TREATMENTS, AND PROCEDURES**

### **7.6.1 PROHIBITED THERAPIES**

No concomitant therapy or investigational therapy aimed at preventing POPF is allowed during the study, including pasireotide.

## **8. STUDY PROCEDURES/EVALUATIONS AND SCHEDULE**

### **8.1 STUDY-SPECIFIC PROCEDURES**

#### **8.1.1 MEDICAL HISTORY**

A medical history will be obtained by the investigator or qualified designee. In addition to collecting information on demographics, the medical history will include all active conditions, and any condition diagnosed within the prior 10 years that are considered to be clinically significant by the Investigator. Details regarding the participant's malignancy, when applicable, will be recorded separately and not listed as medical history (e.g., date of diagnosis, staging).

#### **8.1.2 DISEASE ASSESSMENT**

The investigator or qualified designee will obtain prior and current details regarding the participant's pancreatic cancer.

### 8.1.3 MEDICATION REVIEW

A complete medication history will be acquired concurrent with medical history.

### 8.1.4 PHYSICAL EXAMINATION

Physical exams must be performed by a medically qualified individual such as a licensed physician, Physician's Assistant, or Advanced Registered Nurse Practitioner as local law permits and per institutional standards. The physical examination to be conducted will include an evaluation of: general appearance; head, ears, eyes, nose, and throat; neck; skin; cardiovascular system; respiratory system; gastrointestinal system; lymphatic system, musculoskeletal system, and nervous system. All other physical exams after baseline will include an evaluation of any AEs, or any previously reported symptoms, or prior physical examination findings. All physical examinations will also include:

#### 8.1.4.1 *Vital signs*

Vitals to be collected include blood pressure (BP), heart rate (HR), temperature, and oxygen saturation by pulse oximetry. As part of screening/baseline visit, vitals should be obtained within 10 days prior to first dose of study agent. Vitals will also be obtained during treatment.

Significant findings that were present prior to the signature of the informed consent must be included in the Medical History eCRF page. Significant new findings that begin or worsen after informed consent must be recorded on the Adverse Event eCRF page.

#### 8.1.4.2 *Height and weight*

Height will be collected at screening only. Weight will be collected at each in person visit.

#### 8.1.4.3 *Performance status*

Performance status (Eastern Cooperative Oncology Group) will be determined for all participants at screening.

### 8.1.5 ADVERSE EVENT EVALUATION

Toxicities and adverse experiences will be assessed using the [NCI CTCAE 5.0](#). Safety will be monitored by assessing physical examination, vital signs, body height (screening only) and weight as clinically indicated. Additionally, hematology, chemistry, coagulation, urinalysis, thyroid function, and pregnancy will be assessed as clinically indicated.

Adverse events will be monitored from the time the participant receives treatment on study. Participants will be instructed to report all AEs during the study and will be assessed for the occurrence of AEs throughout the study, including and up to 30 days. Due to the known excellent safety profile of botulinum toxin and FDA-approval for endoscopic injection for achalasia, AEs grade 1-2 will not be collected during the study. AEs Grade 3 or higher must be recorded on the source documents and eCRFs regardless of the assumption of a causal relationship with the study drug.

Abnormal laboratory values will only be recorded as an AE if determined to be clinically significant by the investigator.

For details on AE collection and reporting, refer to Section 10.

## **8.2 LABORATORY PROCEDURES AND EVALUATIONS**

### **8.2.1 HEMATOLOGY**

Only as clinically indicated per institutional standard of care.

### **8.2.2 COMPREHENSIVE METABOLIC PANEL**

Only as clinically indicated per institutional standard of care.

### **8.2.3 COAGULATION PANEL**

Only as clinically indicated per institutional standard of care.

### **8.2.4 PREGNANCY TEST**

A serum or urine pregnancy test is required during screening for all persons of childbearing potential. The pregnancy test is required within 7 days prior to study intervention and results must be available prior to administration of study agent. If the urine pregnancy test is positive, a serum pregnancy test must be performed per institutional standards.

### **8.2.5 AMYLASE ASSAY**

Amylase levels will be drawn from all surgical drains, when present, on postoperative day 3 or 4, per standard of care prior following pancreas resections. In patients undergoing percutaneous drainage of a postoperative intra-abdominal fluid collection, amylase levels on the drained fluid will be drawn to evaluate for crPOPF. An amylase level  $>3$  times the upper limit of normal from a surgical drain is sufficient for diagnosis of POPF, while an amylase level  $>3$  times the upper limit of normal from a percutaneous drain is sufficient for a diagnosis of crPOPF.

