### 1.1.1 OVERVIEW OF STUDY TERMS

**Distal Pancreatectomy.** Distal pancreatectomy (removal of the distal pancreas +/- spleen) is indicated in nonmetastatic PDAC, and other neoplasms when disease is localized in the pancreatic tail, as well as in certain patients with chronic pancreatitis. A variant technique of distal pancreatectomy, termed radical antegrade modular pancreateosplenectomy (RAMPS) is often used specifically for malignancies of the pancreas. Pancreatic surgery is technically difficult and highly morbid, with POPF being the most feared complication by clinicians and patients.

**Postoperative Pancreatic Fistula (POPF).** POPF results when digestive enzymes normally secreted by the pancreas leak into the abdominal cavity following an operation, leading to a wide range of inflammatory and auto-digestive complications. POPF is defined by the International Study Group of Pancreatic Fistula (ISGPF) as an amylase level obtained from drainage fluid or abscess of greater than three times the upper limit of normal, starting from the third postoperative day (POD3). POPF is further classified by the ISGPF into biochemical leaks (asymptomatic elevations in amylase from surgical drain fluid that do not require additional treatment), Grade B POPF (requiring percutaneous or endoscopic drainage), or Grade C POPF (resulting in organ failure); together, Grades B/C constitute clinically-relevant POPF (crPOPF). Rates of POPF following distal pancreatectomy range from 20-50% with an average of 30%, with a 10-year average of at OHSU of 30.9% for all POPF and 11.3% for crPOPF.

[figure not shown]
**Sphincter of Oddi.** The Sphincter of Oddi is a smooth muscle valve located at the Ampulla of Vater that regulates the flow of bile and pancreatic secretions into the duodenum. Following distal pancreatectomy, the resting muscle tone of the Sphincter of Oddi may act as a dam, causing the “path of least resistance” for pancreatic secretions to be the cut edge of the pancreas, resulting in POPF as secretions exit into the abdominal cavity and cause an intense autodigestive and inflammatory reaction.

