### 9.1 DEFINITION OF EFFICACY MEASURES

#### 9.1.1 ANY POPF

Amylase level  $>3x$  the upper limit of normal from a fluid specimen obtained on postoperative day 3 or later, from a surgical drain or intra-abdominal fluid collection.

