#### 9.1.2 CLINICALLY RELEVANT POPF (GRADE B AND C POPF)

1. Amylase level  $>3x$  the upper limit of normal from a fluid specimen obtained on postoperative day 3 or later from postoperatively placed percutaneous or endoscopic drain of an intra-abdominal fluid collection (Grade B POPF).

OR

2. Amylase level  $>3x$  the upper limit of normal from a fluid specimen obtained on postoperative day 3 or later from a surgical drain, postoperatively placed percutaneous or endoscopic drain of an intra-abdominal fluid collection, combined with organ failure clearly attributable to the POPF (Grade C POPF).

Major postoperative complications: Any postoperative complication filling criteria for Clavien-Dindo grade III or higher.

Length of stay: Number of midnights in-hospital following distal pancreas resection

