### 11.5 HANDLING OF MISSING DATA

Every attempt will be made to obtain data at the defined time points as described in the primary and secondary endpoints. If the data are not sufficient to analyze specific endpoints, the participant's data may be excluded entirely or partially. No missing value imputation will be performed.

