#### 13.1.2.1 *National Surgical Quality Improvement Project (NSQIP) & Efficacy Data Collection*

NSQIP is an international initiative sponsored by the American College of Surgeons that records patient demographics, treatment regarding surgical interventions, and captures 30-day postoperative complications data. "Procedure-targeting" allows institutions to capture 100% of certain surgical procedures along with an expanded set of procedure-specific datapoints (e.g., data on POPF and crPOPF for pancreatectomies). OHSU has been procedure-targeting pancreatectomies since 2013.

Data collection for 30-day postoperative complications, including POPF and crPOPF, will be performed by a trained NSQIP surgical clinical reviewer. Due to the workflow of NSQIP reviewers, a lag period between surgery is anticipated equaling up to 3-months. For the purposes of the interim efficacy analysis, subject charts may be reviewed for information relevant to the primary endpoint by individuals other than the NSQIP reviewer. Data obtained from the NSQIP reviewer relating to primary or secondary endpoints will be separately reviewed by a member of the study team and any conflicts or discrepancies resolved. Finalized data will be entered into the EDC system and used for final analysis.

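### For fluid collections drained after surgery, Section 8.2.5 mandates the amylase assay only when drainage is percutaneous, although the primary endpoint in Section 9.1.2 also covers endoscopic drains, so an endoscopically drained fistula may go uncounted if no assay is sent

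*Combined protocol and SAP*

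**What the plan says.** Section 8.2.5 (Amylase Assay) sets two sampling duties. The first covers drains left at operation: "Amylase levels will be drawn from all surgical drains, when present, on postoperative day 3 or 4". The second covers collections drained later: "In patients undergoing percutaneous drainage of a postoperative intra-abdominal fluid collection, amylase levels on the drained fluid will be drawn to evaluate for crPOPF". The section then says what each result establishes. A value above three times the upper limit of normal from a surgical drain establishes POPF, while the same value "from a percutaneous drain is sufficient for a diagnosis of crPOPF". Endoscopic drainage appears in neither the second duty nor the diagnostic sentence.

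Section 9.1.2, which defines the primary endpoint, is wider. Item 1 requires the raised amylase in fluid "from postoperatively placed percutaneous or endoscopic drain of an intra-abdominal fluid collection (Grade B POPF". Item 2 (Grade C) accepts fluid from a surgical drain as well, but only together with organ failure attributable to the fistula. The background in Section 1.1.1 agrees with the wider reading: "Grade B POPF (requiring percutaneous or endoscopic drainage".

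Section 13.1.2.1 covers ascertainment: "Data collection for 30-day postoperative complications, including POPF and crPOPF, will be performed by a trained NSQIP surgical clinical reviewer". A study-team member then reviews the endpoint data separately and discrepancies are resolved. Section 11.5 allows a participant's data to be excluded in whole or part where they are insufficient, and adds: "No missing value imputation will be performed".

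**The concern.** The endpoint names two drainage routes, and the protocol mandates the measurement for one of them. Grade B under Section 9.1.2 is not met by drainage alone; it needs an amylase result from the drained fluid. If a collection is drained endoscopically and the fluid is not assayed, item 1 cannot be shown to be met, whatever the clinical picture. Chart review cannot recover a test that was never run.

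A missing assay can remove an event but cannot add one, so any error favours the intervention. The trial has little room for that, because each Simon decision turns on a single event. One uncounted case turns 2 of 25 (stop) into 1 of 25 (continue), or 3 of 50 (not promising) into 2 of 50 (promising).

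**Working it through.** **Step 1. Compare the routes.**

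| Source of fluid | Assay mandated in 8.2.5? | Named in 8.2.5 as sufficient for crPOPF? | Counts towards crPOPF under 9.1.2? |
|---|---|---|---|
| Surgical drain, day 3 or 4 | Yes | No (POPF only) | Only with organ failure (Grade C) |
| Percutaneous drain placed postoperatively | Yes | Yes | Yes (Grade B) |
| Endoscopic drain placed postoperatively | Not mentioned | Not mentioned | Yes (Grade B) |

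The third row is the gap. The first row does not close it: a patient with a positive surgical drain on day 3 who later has endoscopic drainage without organ failure has a proven POPF under Section 9.1.1, but reaches Grade B under Section 9.1.2 only if the new fluid is assayed. The study schematic places drain fluid analysis at postoperative day 3 only, and no other section mandates the missing assay.

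**Step 2. Reproduce the plan's design.** Inputs from Section 11.2: null rate 0.112, alternative 0.02, 25 participants in stage 1 (continue with 0 or 1 event), 50 in total (promising with 2 or fewer).

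Let b(x) be the binomial probability of x events in 25 at rate p. Then:

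- P(continue) = b(0) + b(1)
- P(promising) = b(0) × P(at most 2 events in the next 25) + b(1) × P(at most 1 event in the next 25)

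At p = 0.112:

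- b(0) = 0.888^25 = 0.0513; b(1) = 25 × 0.112 × 0.888^24 = 0.1618
- P(continue) = 0.2132, so P(early termination) = 0.787 (stated 0.787)
- Expected sample size = 25 + 25 × 0.2132 = 30.33 (stated 30.33)
- P(promising) = 0.0513 × 0.4581 + 0.1618 × 0.2132 = 0.0235 + 0.0345 = 0.058

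At p = 0.02, P(promising) = 0.6035 × 0.9868 + 0.3079 × 0.9114 = 0.876 (stated 0.876).

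The design reproduces. That 0.058 exceeds the stated one-sided 0.05 is a separate matter and no part of this point.

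**Step 3. Illustrate the effect of lost events.** Let f be the share of true crPOPF that is drained endoscopically, has no assay sent, and is then scored as a non-event. If losses are independent, counted events follow a binomial with rate 0.112 × (1 − f). The documents do not give f; the values below are assumptions.

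| f | Counted rate | Expected events lost in 50 (50 × 0.112 × f) | P(early termination) | P(promising) |
|---|---|---|---|---|
| 0% | 0.1120 | 0 | 0.787 | 0.058 |
| 1% | 0.1109 | 0.06 | 0.782 | 0.061 |
| 5% | 0.1064 | 0.28 | 0.761 | 0.072 |
| 10% | 0.1008 | 0.56 | 0.733 | 0.090 |
| 20% | 0.0896 | 1.12 | 0.669 | 0.136 |

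**The case against.** The strongest reply is that Sections 8.2.5 and 9.1.2 do not disagree about what counts. Section 8.2.5 calls a percutaneous result sufficient, which does not make it the only sufficient one. Section 9.1.2 expressly accepts an endoscopic-drain result, and Section 9.1.1 accepts any specimen "from a surgical drain or intra-abdominal fluid collection". Nothing forbids the assay. If routine care sends the fluid, the result counts, and the NSQIP reviewer or the study-team check can find it. All of this stands, and it limits the point to what sampling is mandated.

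A reader might infer more: that Section 8.2.5 takes amylase only after percutaneous drainage, that endoscopically drained fistulas will go uncounted, or that the endpoint cannot be derived for that route. The documents do not support these readings. Surgical drains are sampled too, and loss needs two things together: endoscopic drainage and no assay sent. Neither frequency is given.

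The illustration also treats the 11.2% null as fully ascertained. The documents do not say how endoscopically drained cases were sampled or counted in the historical series. If that series had the same gap, the null already contains the loss and the added inflation is about zero. This stands too, so the figures in the table are scenarios and not estimates.

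What the reply does not answer is the case where no assay is sent. Section 13.1.2.1 gives no rule for classifying an unassayed endoscopic drainage, and Section 11.5 offers only exclusion, without imputation.

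**Conclusion.** The point holds as a gap in mandated sampling for one component of the primary endpoint. Endoscopically drained fistulas may go uncounted if no amylase is sent; whether and how often this would happen cannot be told from the documents. The direction is certain: any loss lowers the counted rate and favours the intervention. The one-event sensitivity of both boundaries does not depend on an assumed frequency. The probabilities do: 0.061 to 0.136 against 0.058 rests on assumed losses of 1% to 20%, independent losses scored as non-events, and a fully ascertained 11.2% null. At the low end the effect is negligible. The mismatch should be corrected because the correction is easy and concerns the primary endpoint, not because a large bias has been shown.

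**What to change.** Amend two sentences of Section 8.2.5. The sampling sentence should cover percutaneous or endoscopic drainage of a postoperative collection, so that fluid from either route is sent for amylase. The diagnostic sentence should say that a result above three times the upper limit of normal from either route is sufficient for crPOPF. Both then match Section 9.1.2, which needs no change.

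The cost is one routine assay on fluid already obtained in a few patients, and possibly a slightly higher observed crPOPF rate. Sample size and decision boundaries stay as they are.

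The amendment should not go further and count unassayed drained collections as Grade B. That would rewrite the primary endpoint, for percutaneous cases as well, and could weaken comparability with the historical rate behind the null.
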